Study Protocol

Official Title: Lithium As a Treatment to Prevent Impairment of Cognition in Elders (LATTICE)

ClinicalTrials.gov ID (NCT number): NCT03185208

Protocol Date: March 12, 2025

Scientific Background

Alzheimer's disease (**AD**) is the most common cause of dementia in adults 65 years and older.¹ AD is a terminal illness that in the run up to death leads to a complete loss of memory and independent function. Unchecked, the disease will reach epidemic proportions in the United States and worldwide by 2050, and presently, there is no intervention that has shown a clear effect on AD progression.² The Alzheimer's Association's 2015 trajectory report estimates that a treatment delaying onset by five years and beginning to show its effect by 2025 would decrease the total number of older Americans with AD from 8.2 to 5.2 million by 2030.³ Additionally, a treatment that slows disease progression will also result in far fewer AD patients in the most severe stage that requires the highest level of care with the greatest cost.³ Hence, there is an urgent need to find treatments from pre-symptomatic to symptomatic AD to meet this looming challenge. This work aims to meet this challenge.

Over the past several years, there has been increasing interest in repurposing the use of lithium for diseases involving neurodegeneration.⁴ Lithium treatment has been associated with neurogenesis in the hippocampus,⁵ up-regulation of important neurotrophic factors such as B-cell lymphoma 2 (**Bcl-2**) and brain-derived neurotrophic factor (**BDNF**),⁶ and, relevant to this project, inhibition of glycogen synthase kinase 3 (**GSK-3**) isoforms α and β . In particular, GSK-3 α interacts with gamma-secretase playing a critical role in the conversion of amyloid precursor protein (**APP**) to amyloid-beta (**A β**); lithium has been shown to reduce A β production and memory deficits in AD transgenic mouse models.⁷ GSK-3 β phosphorylates tau, a critical step in the formation of neurofibrillary tangles, and lithium has been shown to reduce tau phosphorylation *in vivo* and *in vitro*.⁸ That lithium may alter the AD trajectory is supported by numerous observational reports showing delay of dementia onset in those treated with it.⁹⁻¹³ *However, the results of the few human lithium trials conducted have been mixed.*¹⁴⁻¹⁷ At this time, it is difficult to draw definitive conclusions and make recommendations for widespread use of lithium based on the current evidence as well as the unclear risk/benefit profile of lithium treatment in older adults at risk for developing AD. Research is needed to determine whether lithium has a role as an anti-dementia agent. In contrast to previous studies, we will implement an RCT with a more integrative, comprehensive approach than done before involving state-of-the-art ultra-high field (7T) human MRI, neurocognitive assessment, and blood-/CSF- based biomarker measurement to investigate the role of lithium as an anti-dementia agent.

The rate of conversion to dementia among older adults with mild cognitive impairment (**MCI**) is 15% per year in clinic samples.¹⁸ Accordingly, we will enroll older adults who meet criteria for MCI in which we will assess whether lithium can alter the AD trajectory.¹⁹ Enrolling individuals who exhibit no cognitive impairment would be the basis of a different, much larger and longer study given the lower rates of AD conversion compared with individuals with MCI. Conversely, enrolling individuals with established AD is likely too far in the disease process for lithium to make a significant difference.

Study Objectives

Specific Aim: To examine the potential disease modifying properties of lithium in individuals with MCI in delaying conversion to dementia.

H1: a) Participants randomized to take lithium for two years, compared to placebo, will better maintain cognitive function, primarily in memory, which b) will be associated with changes in biomarkers (e.g., GSK-3 β activity, BDNF).

H2: a) Participants randomized to take lithium for two years, compared to placebo, will have larger hippocampal volumes and lower total gray matter thinning, which b) will be associated with changes in biomarkers (e.g., GSK-3 β activity, BDNF) and c) better cognitive function, primarily in memory.

Exploratory Aim: To examine whether lithium is related to additional markers of enhanced brain integrity (e.g., lower level of microbleeds, higher white matter integrity, better network connectivity, or decreased CSF phospho tau levels).

Study Design & Methods

Enroll and randomly assign 80 individuals 60 years and older with MCI to take lithium, titrated as tolerated to a blood level of 0.6 to 0.8 mEq/L, or placebo for two years to assess lithium's effects on preserving cognition and delaying conversion to dementia. Participants will receive annual neurocognitive assessment, ultra-high field (7T) brain MRI (e.g., high-resolution imaging of hippocampal and total cortical gray volumes, white matter integrity, dynamic imaging), blood- (e.g., GSK-3 β , BDNF, cytokines) and CSF-based (e.g., A β , total tau, and phospho tau) biomarker measurement. All subjects will undergo baseline PET imaging of A β on which to stratify randomization. *This study is powered to detect medium/large effect sizes for H1-2, and will serve as the “go/no-go” for a subsequent, larger-scale, confirmatory study.*

Eligibility Criteria

Inclusion criteria:

1. 60 years or older
2. Diagnosis of Mild Cognitive Impairment

Exclusion criteria:

1. Major psychiatric illness (mild psychiatric illness may be included)
2. Major neurologic illness (e.g., multiple sclerosis)
3. Contraindication to lithium (e.g., renal insufficiency)
4. Unable to complete neuropsychological testing due to non-remediable impairment (e.g., blindness)

Statistical Considerations

HYPOTHESIS TESTING. All statistical analyses will be conducted starting with basic descriptive techniques and two sample testing (t-tests, Wilcoxon tests, chi-square tests) for testing the difference between the intervention and control groups. Statistical tests will be two-sided and interpreted at the 0.05 level. We have also performed all of our power computations and have provided effect sizes for all adjusted analysis (p<0.01) due to multiple testing. Additionally, all of our voxel-wise analyses results will be corrected using FWE. These analyses will then inform the next step in the analysis process that will include statistical modeling. First, adherence will be assessed over time by intervention group using a Kaplan-Meier approach where non-adherence is considered to be an "event." For all modeling, we will use regression diagnostics to identify potential outliers or influential observations. Additionally, the analyses will be assessed for the impact of missing data. For the initial reporting of all results, we will follow the guidelines outlined in the CONSORT statement and follow intention to treat principles: subjects will continue to be followed and analyzed according to the original randomized assignment.^{134, 135} Tests of whether missingness is at random will be performed. Should missing data prove to be an issue, we will rely on inverse probability weighting or imputation as part of the analysis.

Specific Aim: H1-2. This analysis focuses on assessing the effect of lithium on: (H1) cognitive performance and, (H2) neuroimaging measures of hippocampal volumes and total gray matter and cognition. Outcomes are measured at three time points, and our primary analysis will consist of linear mixed effects models. These models will include a term for time, group and a time-by-group interaction. We will test for lithium effect by testing the significance of the coefficient associated with the interaction term in the model as well as by a likelihood ratio test between the models with and without interaction. First, we will fit these basic models for each of the outcomes of interest and test for the time-by-group interaction as an assessment of the effect of lithium. Second, we will include potential covariates (e.g., age, education, sex, etc.) and exploratory covariates (e.g., physical activity) that may influence the group effect and test for a time-by-group interaction in this context. We will examine the biomarker trajectories across the two groups. If the assays used to measure the biomarkers produce results outside of the detectable limits, we will use tobit model and mixed model extensions of the tobit model to test for differences between the two groups.

POWER ANALYSIS. For H1a/H2a, where 80 subjects will be randomized to one of two groups with 64 completers (32 in each cell), we computed power based on the following assumptions: a two-sided significance level of 0.05, a power of 0.80 and measurements at three time points for a repeated measures model. Based on these assumptions, we are powered to observe an effect size (Cohen's **d**) of 0.57 (i.e., medium) when the observations are correlated at a level of 0.5 across time. The effect size ranges from 0.45 to 0.60, a little over a half standard deviation difference in the outcome variable, as the correlation between repeated observations ranges from 0.1 to 0.6. We also computed the effect size for a two-sided significance level of 0.01, a more conservative alpha for testing multiple outcomes, and power of 0.80 as above and found that the effect size ranged from 0.54 to 0.72 as the correlation between repeated observations ranged from 0.1 to 0.6.

References

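### The planned test of whether missingness is at random cannot be done from observed data, and the plan specifies no analysis that departs from that assumption

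*Combined protocol and SAP*

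**What the plan says.** Four statements in the HYPOTHESIS TESTING paragraph of Statistical Considerations bear on missing data.

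- A general intent: "the analyses will be assessed for the impact of missing data". No method is attached.
- An intention-to-treat commitment: "subjects will continue to be followed and analyzed according to the original randomized assignment".
- A test: "Tests of whether missingness is at random will be performed". No procedure, null hypothesis or variables are named.
- A conditional fallback: "Should missing data prove to be an issue, we will rely on inverse probability weighting or imputation as part of the analysis". No trigger or model is given.

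The same paragraph starts with two-sample tests (t, Wilcoxon, chi-square). The Specific Aim: H1-2 paragraph makes linear mixed models the primary analysis: "These models will include a term for time, group and a time-by-group interaction". A second step adds covariates: "Second, we will include potential covariates (e.g., age, education, sex, etc.) and exploratory covariates". Tobit models are planned only for biomarker values outside assay limits. The POWER ANALYSIS paragraph assumes "80 subjects will be randomized to one of two groups with 64 completers (32 in each cell", that is, 16/80 = 20% non-completion, equal by arm.

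**The concern.** MAR and MNAR differ only in how missingness depends on values nobody has seen. Without untestable modelling assumptions, no test on the observed data can tell them apart. A comparison of participants with and without missing data can give evidence against MCAR, but a non-significant result says nothing about MNAR. If an MCAR check was meant, the sentence mislabels it. If a test of MAR was meant, it cannot work.

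The other named methods do not fill the gap. The mixed model, its covariate-adjusted version, and weighting or imputation in standard form are valid under MAR given the variables used. The initial two-sample tests on observed cases generally need more than that. All of them could agree and share the same bias.

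The outcome is cognition in people with mild cognitive impairment, and the active drug is titrated according to tolerability, so reasons for leaving may differ by arm. The study is to serve as the go/no-go for a confirmatory trial. A report that missingness had been tested and found to be at random would present an untestable assumption as checked.

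**Working it through.** **1. Does any specified method depart from MAR?**

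| Method in the plan | Assumption about missing outcomes |
|---|---|
| Two-sample tests on observed cases | Generally stronger than MAR |
| Mixed model with time, group and interaction | MAR given observed outcomes and arm |
| Mixed model with added covariates | MAR given those covariates as well (weaker, still MAR) |
| Inverse probability weighting, imputation (standard form) | MAR given the variables in the weighting or imputation model |
| Tobit models | Concern assay limits, not dropout |

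No delta-adjusted, reference-based, pattern-mixture, selection-model or tipping-point analysis appears.

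**2. Reproducing the plan's own figure.** With 32 per arm, three measurements and correlation 0.5, the average-over-visits contrast gives

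d = (1.960 + 0.842) × √[(2/32) × (1 + 2 × 0.5)/3] = 2.802 × 0.204 = 0.572,

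against the stated 0.57. Over correlations 0.1 to 0.6 it gives 0.443 to 0.600 at alpha 0.05 (stated 0.45 to 0.60) and 0.540 to 0.732 at alpha 0.01 (stated 0.54 to 0.72). So 0.57 is an effect on the average over visits, with SE 0.204. The planned test is of the time-by-group interaction, so the rest uses the year-2 difference in change.

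**3. Size of the problem (illustration).** From the plan: 80 randomised, 64 completers, correlation 0.5, two-sided alpha 0.05. Assumed: delta, the amount by which unseen year-2 values are worse than MAR predicts, in SD units. The documents fix neither its size nor its direction.

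- SE of the difference in change = √[2(1 − 0.5)] × √(2/n). With n = 32 (20% missing) this is 0.250; with n = 36 (10% missing) it is 0.236.
- Bias = (share missing × delta) in the lithium arm minus the same product in the placebo arm.
- Error = P(|Z + bias/SE| > 1.96).

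| Scenario | delta 0.3 | delta 0.5 | delta 0.75 |
|---|---|---|---|
| 20% missing, lithium only: bias/SE | 0.24 | 0.40 | 0.60 |
| Two-sided error | 5.7% | 6.9% | 9.2% |
| 10% missing, lithium only: error | 5.2% | 5.5% | 6.2% |
| 20% missing, placebo shifted half as much: error | 5.2% | 5.5% | 6.0% |
| 20% missing, equal shifts: error | 5.0% | 5.0% | 5.0% |

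The planned linear-time mixed model with all 40 per arm, 8 per arm missing year 2 and variance treated as known, has SE 0.241. The first error row then becomes 5.7%, 7.0% and 9.6%, so the completer approximation is adequate.

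*Placebo-only shift, 20% missing.* A true difference of 0.70 SD has power P(Z > 1.96 − 0.70/0.25) = 80%. With the difference reduced by 0.2 × delta, power is P(Z > 1.96 − (0.70 − 0.2 × delta)/0.25) = 73%, 67% and 59.5%.

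*Unequal dropout.* With 30% missing on lithium and 10% on placebo (still 28 + 36 = 64 completers), the same 0.5 SD shift in both arms gives a bias of 0.30 × 0.5 − 0.10 × 0.5 = 0.10 SD.

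**4. What a tipping-point analysis would show.** For an observed 0.70 SD difference in change and a lithium-only shift, ignoring added imputation variance:

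- 20% missing: (0.70 − 1.96 × 0.250)/0.2 = 1.05 SD.
- 10% missing: (0.70 − 1.96 × 0.236)/0.1 = 2.4 SD, a robust result that no named analysis would reveal.

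**The case against.** *The test sentence may be loose wording for an MCAR check.* Possibly, but it still has to be corrected, because a reader would take a passed test as support for MAR.

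*The plan does commit to assessing the impact of missing data, and imputation can be done under MNAR.* Both are true. A reader might infer that the plan ignores the issue or rules out such an analysis. It does neither. The accurate charge is that no departure from MAR is specified, so the commitment could be met entirely by analyses that share the assumption.

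*Covariates help.* They weaken the assumption. In a large simulated example where dropout is driven by the unseen score itself, adding a covariate correlated 0.5 with it still left an unseen shift of 0.46 to 0.60 SD. If dropout depends on the covariate alone, the bias disappears.

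*Follow-up continues after treatment stops, so fewer than 20% of outcomes may be missing.* This stands, and the 10% row is much milder.

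*The study is small and precedes a confirmatory trial.* This is a fair reason to keep the addition to one analysis of one outcome. It does not rescue a test that cannot answer its question.

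*A reader might pair the plan's 0.57 with the year-2 change SE of 0.25 and conclude that a positive result would be fragile.* The documents do not support that. The figure reproduces as an average-over-visits effect with SE 0.204, so the pairing mixes two contrasts.

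**Conclusion.** The sentence promising a test of MAR is wrong as written. The missing tipping-point analysis is a cheap improvement to a plan that states the right intent without a method.

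The effect is modest unless the shift or the dropout differs by arm. With equal dropout and equal shifts the error stays at 5.0%. The worst case shown is 9.2%, and it needs 20% missing and a 0.75 SD shift confined to the lithium arm. These figures rest on correlation 0.5, normal approximations and assumed deltas.

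Two stronger readings are not supported. A reader might infer that the lithium result will be biased in lithium's favour; the documents do not fix the direction, and a placebo-only shift costs power instead. A reader might also take the error rates as rates of a wrong go decision. The protocol says the study will serve as the go/no-go but states no p-value rule for it, so these are error rates of the test only.

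**What to change.** Replace the last two sentences of the HYPOTHESIS TESTING paragraph with:

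> Baseline and earlier outcomes will be compared between participants with and without missing data, by arm, as a check of MCAR only. The primary mixed model uses all observed data from all randomised participants and assumes MAR; inverse probability weighting or multiple imputation, using a small prespecified set of collected variables, is a sensitivity analysis under MAR. Whatever the dropout pattern, a delta-adjusted tipping-point analysis will be reported for the memory outcome prespecified for H1a, with delta (in baseline SD units of that outcome) varied separately by arm, in both directions, from 0 upward until the conclusion changes or to a stated limit of at least 1.5 SD; if it does not change by the limit, that will be reported.

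Both sentences need replacing. Deleting only the conditional clause would make weighting or imputation unconditional and leave its relation to the primary mixed model unclear. The text also requires one memory outcome to be named for H1a, because the plan refers only to memory in general. Keep the variable set small, since about 16 non-completers cannot support a long weighting model. Baseline amyloid and adherence, which the plan already assesses ("First, adherence will be assessed over time by intervention group using a Kaplan-Meier approach"), are candidates.

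The cost is plan wording and one imputation analysis over a grid of deltas, with no new data or visits. The downside is a little more analysis work, and a positive result may have to be reported as less robust.

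### Setting a common baseline mean in the primary mixed model would cut the variance of the two-year lithium effect by about 21% at correlation 0.5 and 17% at 0.6, with no new data

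*Combined protocol and SAP*

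**What the plan says.** Study Design & Methods sets out a randomised comparison: "Enroll and randomly assign 80 individuals 60 years and older with MCI to take lithium" or placebo for two years. On timing it says "Participants will receive annual neurocognitive assessment".

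Statistical Considerations, Specific Aim: H1-2, states: "Outcomes are measured at three time points, and our primary analysis will consist of linear mixed effects models". I read the three time points as baseline, year 1 and year 2. On the model terms it says "These models will include a term for time, group and a time-by-group interaction". Lithium is to be assessed by "testing the significance of the coefficient associated with the interaction term in the model as well as by a likelihood ratio test" comparing the models with and without the interaction. In a second step, "we will include potential covariates (e.g., age, education, sex, etc.) and exploratory covariates (e.g., physical activity) that may influence the group effect". Baseline score is not among the named covariates, and nothing in the document sets the arms' baseline means equal.

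The analysis follows intention to treat: "subjects will continue to be followed and analyzed according to the original randomized assignment". The Power Analysis assumes "80 subjects will be randomized to one of two groups with 64 completers (32 in each cell") and correlations between repeated measurements of 0.1 to 0.6, with 0.5 as its central case.

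**The concern.** With baseline in the outcome vector and a group term in the model, the interaction is judged against each arm's own estimated baseline mean. Chance imbalance at baseline then adds variance that randomisation entitles the analysis to remove. A shared baseline mean, or adjustment for baseline score, removes it.

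This does not inflate type I error, and no stated figure is wrong because of it. The cost is precision, and it matters because the trial is small and is described as the go/no-go for a larger confirmatory study. A real effect missed here could end the programme.

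**Working it through.** **Inputs.** From the Power Analysis: 80 randomised (40 per arm if allocation is equal), 32 completers per arm, three measurements, two-sided alpha 0.05 (also 0.01), power 0.80, correlation rho 0.1 to 0.6. Assumed: SD 1; compound symmetry, because the plan gives a single correlation; and the 8 non-completers per arm contribute baseline only. The last two are varied below.

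**The plan's own figure.** The stated effect size reproduces as a time-averaged group difference:

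d = (1.960 + 0.842) × √[(2/32)(1 + 2rho)/3]

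At rho 0.5 this is 2.802 × √(0.0625 × 0.6667) = 0.572 (stated 0.57). At rho 0.1 and 0.6 it is 0.443 and 0.600 (stated 0.45 and 0.60). At alpha 0.01 the range is 0.540 to 0.732 (stated 0.54 to 0.72). Agreement is close, but this is not the interaction the plan tests, so the comparison below uses the two-year effect: the difference between arms in change from baseline to year 2.

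**Variance of the two-year effect, categorical time, all 80 analysed.**

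- Free baseline means: (2/32)(1 − rho²) + (2/40)(1 − rho)²
- Common baseline mean: (2/32)(1 − rho²)

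At rho 0.5: 0.046875 + 0.0125 = 0.059375 against 0.046875. The ratio is 0.789, a cut of 21.1%.
At rho 0.6: 0.040 + 0.008 = 0.048 against 0.040, a cut of 16.7%.

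| rho | SE, free | SE, common | Variance cut |
|---|---|---|---|
| 0.1 | 0.3200 | 0.2487 | 40% |
| 0.5 | 0.2437 | 0.2165 | 21% |
| 0.6 | 0.2191 | 0.2000 | 17% |
| 0.8 (assumed) | 0.1565 | 0.1500 | 8% |
| 0.9 (assumed) | 0.1112 | 0.1090 | 4% |

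If the planned model uses linear time, as its reference to a single coefficient suggests, its SE is 0.2436 at rho 0.5 and 0.2190 at 0.6. Against the recommended categorical model the loss is the same.

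**What this means for the trial.**

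- Detectable two-year difference, (z[1−alpha/2] + z[0.80]) × SE. At alpha 0.05: 2.802 × 0.2437 = 0.68 SD falls to 2.802 × 0.2165 = 0.61 SD (rho 0.5), and 0.61 falls to 0.56 SD (rho 0.6). At alpha 0.01, rho 0.5: 0.83 falls to 0.74 SD.
- Equivalent number randomised under the planned model: 80 × 0.059375/0.046875 = 101 (rho 0.5); 80 × 0.048/0.040 = 96 (rho 0.6).
- Power for an illustrative 0.57 SD two-year difference, alpha 0.05, normal approximation: 65% to 75% (rho 0.5), 74% to 81% (rho 0.6). The plan's 0.57 belongs to a different contrast, so these are not the trial's power.

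**Sensitivity.**

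- Dropout timing: the cut stays at 21% and 17% (rho 0.5 and 0.6) if 4 or all 8 dropouts per arm also have year 1. Completers only gives 25% and 20%.
- Random slopes added (assumed slope variance 0.04 to 0.2): 18% down to 11% at rho 0.5; 14% down to 8% at rho 0.6.
- AR(1) with that one-year correlation: 32% and 27%.

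**Small-sample check.** Simulation with unstructured covariance, REML and 20,000 trials per cell compared free with common baseline. Type I error with Kenward-Roger was 0.050 and 0.050 (rho 0.5), 0.049 and 0.052 (rho 0.6). With Wald z it was 0.056 and 0.058, then 0.052 and 0.059. Kenward-Roger power at 0.57 SD rose from 62% to 72% and from 73% to 79%.

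**The case against.** The planned model is conventional and valid, so this can be called a design preference. That is fair as to kind. It is why the point is a recommended improvement and not an error.

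The 21% and 17% rest on compound symmetry. The plan uses a single correlation for its power calculation but does not state the covariance structure of the primary model. If participants decline at different rates, the gain is nearer the random-slope figures. This stands as a limit on size; every structure examined still shows a gain.

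The imaging outcomes in H2 may gain little. At rho 0.8 and 0.9 combined with the same random slopes, the cut is only 2.7-5.8% and 0.8-2.2%. The documents give no correlation above 0.6, so whether volumes behave this way is unknown. If they do, the change matters mainly for cognition (H1).

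The fix does more than drop one term: if the plan meant linear time, the test moves from a slope difference to a year-2 contrast. That is true, but a common baseline with linear time makes the estimate depend on the shape of the effect. At rho 0.5 with baseline-only dropouts it returns 0.91 of a two-year effect that appears only at year 2, and 1.09 of one that plateaus at year 1 (0.86 and 1.14 if all dropouts have year 1). The planned model with linear time has a smaller version of the same problem (0.983 and 1.017 with baseline-only dropouts).

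The covariate list is open-ended, so baseline score could enter the second-step model. It is not named, and the first-step model has no covariates.

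**Conclusion.** The concern holds as an efficiency point that should be acted on. The primary model forgoes precision that randomisation supplies at no cost in data. At the correlation the protocol itself uses, 0.5, the standard error of the two-year effect would fall by 11% (9% at 0.6). This rests on compound symmetry and on all 80 being analysed. The assumed timing of dropout hardly affects it; the covariance structure does, so a fair reading at correlations of 0.5 to 0.6 is a variance cut from about 8% (steepest assumed random slopes, 0.6) to 32% (AR(1), 0.5). The conclusion does not depend on the simulation, which serves to support the choice of a small-sample method.

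**What to change.** Before any unblinded data are seen, replace the primary model with wording such as:

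> Categorical time plus time-by-group at years 1 and 2, with no group main effect (one common mean for a baseline outcome measured before study treatment starts); unstructured covariance; all randomised participants included; REML with Kenward-Roger standard errors and degrees of freedom. The lithium effect is the 1-df contrast at year 2.

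- Do not apply the constraint to any outcome whose baseline was measured after treatment began.
- If the likelihood ratio test is kept, state that it has 2 df with categorical time, base it on ML fits, and label it supportive.
- Modelling years 1 and 2 with baseline score and baseline-by-time as covariates is a close alternative.
- Keep the unconstrained model as a sensitivity analysis.
- State how the amyloid PET stratification factor enters the model; it was not part of these calculations.

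The cost is a short, dated change to the specification, with no additional participants, visits or assays. The documents do not say what stage the trial has reached, so confirm first that unblinding has not occurred.

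### The primary mixed model leaves out the amyloid stratum used in randomisation and states no random effects: a small likely loss of power, and an error rate that depends on the unstated covariance

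*Combined protocol and SAP*

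**What the plan says.** Study Design & Methods: "All subjects will undergo baseline PET imaging" for amyloid-beta, "on which to stratify randomization". Amyloid positivity is not an entry criterion, so both positive and negative participants can be enrolled.

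Statistical Considerations, Specific Aim: H1-2: "our primary analysis will consist of linear mixed effects models", and "These models will include a term for time, group and a time-by-group interaction". The lithium effect is tested on that interaction. A second step follows: "Second, we will include potential covariates (e.g., age, education, sex, etc.) and exploratory covariates (e.g., physical activity", after which the interaction is tested again. The amyloid stratum is named in neither step. No random intercept, random slope or covariance structure is given.

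Power Analysis: 80 randomised, "with 64 completers (32 in each cell", three time points, and a range of detectable effects "as the correlation between repeated observations ranges from 0.1 to 0.6". Hypothesis Testing: "Statistical tests will be two-sided and interpreted at the 0.05 level".

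**The concern.** Stratified randomisation balances amyloid status between the arms. If amyloid-positive and amyloid-negative participants decline at different rates, that balance makes the treatment contrast more precise. The analysis gets the benefit only if the model removes the same variation from the error term. A model with time, group and time-by-group alone leaves it there, so the standard error of the slope difference is larger than it need be.

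The term that matters is stratum-by-time. With complete balanced data, a stratum main effect alone leaves a slope contrast unchanged.

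The missing random-effects statement belongs to the same specification. It decides whether person-to-person variation in slope is counted as error at all, and hence whether the test holds its 5% level. At stake are a somewhat wider confidence interval and an error rate that is not fixed in advance, in a small trial meant to support a go/no-go decision.

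**Working it through.** **Inputs from the documents.** Two-sided alpha 0.05, power 0.80, 32 completers per arm, three measurements, correlation rho = 0.5 (range 0.1 to 0.6). Annual assessment over two years gives visits at years 0, 1 and 2.

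**Assumptions, not in the documents.** Outcome SD 1; time linear; two strata with a share p = 0.5 positive, 16 per cell; complete data. D is the slope difference between amyloid strata in SD per year. tau2 is slope variance from other sources.

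**1. The plan's own figure.** A time-averaged group difference under a common correlation gives d = 2.8016 × sqrt((2/32) × (1 + 2 rho)/3). At rho = 0.5 this is 2.8016 × sqrt(0.0625 × 2/3) = 0.572 (stated 0.57). At rho = 0.1 and 0.6 it is 0.443 and 0.600 (stated 0.45 to 0.60; 0.450 at the low end with a t correction). The stated figure therefore reproduces, but as an averaged difference and not as a slope difference. The power values below are calibrated separately.

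**2. Variance inflation.** The variance of a person's fitted slope within strata is (1 − rho)/2 + tau2, which is 0.25 at rho = 0.5, tau2 = 0 and 0.35 at tau2 = 0.10. Leaving out stratum-by-time inflates the estimated variance by

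I = 1 + p(1 − p)D² / ((1 − rho)/2 + tau2).

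Example, D = 0.40, tau2 = 0: 1 + 0.25 × 0.16/0.25 = 1.16.

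**3. Power and type I error with slope variance modelled.** The treatment slope difference is set so that the adjusted test has 80% power by normal approximation: 2.8016 × sqrt(0.25 × 4/64) = 0.350 SD/year at tau2 = 0, and 0.414 at tau2 = 0.10. Unadjusted power is then approximately Phi(2.8016 − 1.96 × sqrt(I)). At I = 1.16 this is Phi(2.8016 − 2.111) = 75.5%, and type I error is 2 × (1 − Phi(2.111)) = 3.5%. Simulated two-sided t-tests on person slopes (40,000 trials per setting; 62 df unadjusted, 61 df adjusted) give:

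| D | tau2 | I | Power unadjusted | Power adjusted | Loss (points) | Type I, unadjusted |
|---|---|---|---|---|---|---|
| 0.15 | 0 | 1.023 | 78.4% | 79.0% | 0.6 | 4.6% |
| 0.15 | 0.10 | 1.016 | 78.2% | 78.7% | 0.5 | 4.9% |
| 0.25 | 0 | 1.063 | 77.0% | 79.0% | 2.0 | 4.4% |
| 0.25 | 0.10 | 1.045 | 77.5% | 78.8% | 1.3 | 4.5% |
| 0.40 | 0 | 1.160 | 73.8% | 78.7% | 4.9 | 3.6% |
| 0.40 | 0.10 | 1.114 | 75.3% | 78.7% | 3.4 | 3.8% |

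Adjusted type I error is 4.9% to 5.1%. The unadjusted confidence interval is wider by a factor of 1.008 to 1.079.

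**4. Sensitivity.** Over rho 0.1, 0.5 and 0.6 and tau2 from 0 to 0.20, the loss is 0.2 to 0.8 points at D = 0.15, 0.7 to 2.5 at D = 0.25 and 1.9 to 6.4 at D = 0.40. With 30% or 70% positive, I − 1 shrinks by 0.21/0.25 = 0.84. At D = 0 nothing is lost.

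**5. Random intercept only, while slopes vary.** The model pools the linear and quadratic within-person contrasts, so the true variance exceeds the assumed one by ((1 − rho) + 2 tau2) / ((1 − rho) + tau2 + u), where u = p(1 − p)D² if the stratum is left out and 0 if it is adjusted for. Adjusted, rho = 0.5: tau2 = 0.05 gives 0.60/0.55 = 1.091 and type I error 2 × (1 − Phi(1.96/sqrt(1.091))) = 6.1%; tau2 = 0.20 gives 0.90/0.70 = 1.286 and 8.4%. Simulation over tau2 0.05 to 0.20 and D 0.15 to 0.40 gives 5.2% to 8.4% unadjusted and 6.1% to 8.6% adjusted.

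**6. Check with fitted mixed models.** REML with random intercept and slope (2,000 trials per setting, tau2 = 0.10) gives power of 77.6% unadjusted and 79.1% adjusted at D = 0.25, and 76.1% and 79.1% at D = 0.40. At tau2 = 0 and D = 0.40 it gives 72.5% and 76.5%.

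**The case against.** The strongest reply is that the plan's power calculation assumes one common correlation, which corresponds to a random intercept. If that holds (tau2 = 0), the plan's basic model with a random intercept already has 79.0%, 78.9% and 77.0% power at D = 0.15, 0.25 and 0.40. The adjusted slope test has 79.0%, 79.0% and 78.7%, and the adjusted REML model only 76.5% at D = 0.40. This stands: in that case the proposed model gains little or nothing, and the random slope has a price. What it buys is protection of the 5% level if slopes do vary, which the plan cannot know in advance.

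Secondly, the second-step covariate list is open and could include amyloid. That also stands, so it would be wrong to say the plan rules the adjustment out. But the stratum is not named, and the plan does not say which step decides.

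Thirdly, the figures have limits. They are for complete data on 64 people; dropout among the 80 was not simulated. With tau2 above 0, SD 1 and rho 0.5 describe only baseline and the part without slope variation. With independent intercepts and slopes, tau2 = 0.10 gives a year-2 variance of 1 + 4 × 0.10 = 1.4 and a year 0 to year 2 correlation of 0.5/sqrt(1.4) = 0.42. These limits affect the exact sizes more than the direction.

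A reader might also set the 0.40 SD/year case against the plan's d of 0.57. The two are not comparable: one is a slope difference, and the other reproduces only as a time-averaged difference.

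**Conclusion.** The concern holds, with minor weight. The stratification factor is missing from the stated model terms and the random effects are unspecified. With slope variance modelled, and half positive, rho 0.5 and 32 completers per arm, the likely cost is about 0.5 to 2 points of power at amyloid slope differences of 0.15 to 0.25 SD/year, and about 3 to 5 points at 0.40. These inputs are assumed. If amyloid does not predict slope, the cost is nil.

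A reader might infer that leaving out the stratum biases the lithium effect or raises the false-positive rate. It does neither under these conditions: stratified allocation keeps the estimate unbiased, and the test is conservative (3.6% to 4.9%). Error rates above 5% come from a random-intercept-only model when slopes vary (about 5% to 8.5%), and adding the stratum does not cure that. Nor is the loss a shortfall from the planned 80%. It is relative to the adjusted test, at an effect size chosen for this comparison.

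**What to change.** In the first-step primary model, specify fixed effects for amyloid stratum (as recorded at randomisation), time, stratum-by-time, group and time-by-group, with a random intercept and a random slope for time, or an unstructured within-person covariance. Keep the test on time-by-group. Make both changes together, before unblinding.

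Cost: one line of text, no new data (baseline PET is planned for everyone) and about two degrees of freedom if there are two strata. The random slope is not free. If slopes do not otherwise vary, it can cost about 2 points of power (at D = 0.40 and tau2 = 0, 78.7 − 76.5 = 2.2 between the adjusted slope t-test and the adjusted REML model). That is the price of protecting the 5% error rate. The unstructured alternative was not checked numerically here.
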